**Table 7. Disease-Free Survival by Independent Review Committee Using a Parametric Model for Interval-Censored Data**

**Censoring Rules:**

|   |  | Date of event*/ censoring   | Censoring |
|---|--|--|------------------|
| No IRC confirmed recurrence or occurrence of secondary malignancy | Post baseline assessments performed  | Date of last IRC reviewed scan prior to receiving anti-tumor therapy if applicable   | Yes              |
|   | No post baseline assessments performed   | Date of randomization  | Yes              |
| IRC confirmed recurrence or secondary malignancy or death         | Baseline scan shows presence of disease  | Date of randomization  | No               |
|   | Further anti-tumor therapy received after randomization and before recurrence or occurrence of secondary malignancy or death (Subject did have two or more consecutively missed/not readable IRC reviewed scans)     | Date of midpoint between last IRC reviewed scan prior to receiving anti-tumor therapy and before two consecutively missed/not readable IRC reviewed scans and date of IRC confirmed recurrence or secondary malignancy or death      | Yes              |
|   | No anti-tumor therapy received after randomization (Subject did have two or more consecutively missed/not readable IRC reviewed scans)   | Date of midpoint between last IRC reviewed scan prior to two consecutively missed/not readable scans where there was no IRC confirmed recurrence and date of IRC confirmed recurrence or occurrence of secondary malignancy or death | Yes              |
|   | Further anti-tumor therapy received after randomization and before recurrence or occurrence of secondary malignancy or death (Subject did not have two or more consecutively missed/not readable IRC reviewed scans) | Date of midpoint between last IRC reviewed scan prior to receiving anti-tumor therapy and date of IRC confirmed recurrence, occurrence of secondary malignancy or death  | Yes              |
|   | No anti-tumor therapy received after randomization (Subject did not have two or more consecutively missed/not readable IRC reviewed scans)   | Date of IRC confirmed recurrence or occurrence of secondary malignancy or death  | No               |

Document: C:\Users\q764206\AppData\Local\Microsoft\Windows\Temporary Internet Files\Content.Outlook\GWW33WM3\ATLAS\_SAPFinal v8.0\_06MAR2018.docx  
 Author: [name] (Updated [name]; [name]; [name], [name]) Version Number: Final 8.0  
 Version Date:

06MAR2018

Template No: CS\_TP\_BS016 – Revision 2  
 Effective Date: 01Feb2010

Reference: CS\_WI\_BS005

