#### Footnotes for Schedule of Assessments

- imaging should be repeated every 6 months for the duration of the DFS follow-up period. Additional imaging of potential disease sites should be performed whenever recurrence or occurrence of a secondary malignancy is suspected. Bone scan (confirmatory imaging in addition to bone scan may be required), if clinically indicated.
- 15. **Histo-/cytopathology:** Local histopathology confirmation of eligibility is required. After randomization, in cases for which there is site confirmation of recurrence or occurrence of a secondary malignancy in the absence of IRC imaging confirmation, available local histo-/cytopathology reports should be submitted to the IRC for review.
- 16. **Study Randomization**: Patients must be randomized by 12 weeks after nephrectomy. Patient eligibility must be confirmed by IRC review for imaging and by a sponsor designated laboratory. Patients must be randomized based on the assessment by the IRC when there is a discrepancy between the local and the IRC imaging review.
- 17. **Study Treatment**: Should be started within 7 days after randomization. It is not necessary to repeat the Day 1 procedures if treatment is not started on the same day as randomization. Patients will receive either axitinib tablets at a starting dose of 5 mg BID or placebo according to randomization. The axitinib/placebo dose may be adjusted up or down according to individual patient tolerance per protocol dose modification procedure. Study drug are dispensed on Day 1 of each cycle.
- 18. **Adverse Events (AEs)**: Will be collected from the first day of study treatment until at least 28 days after the last on-study drug administration (Allowable window for assessment is 0/+7 days.), or until all serious or study drug-related toxicities have resolved or are determined to be "chronic" or "stable," whichever is later. Serious adverse events should be monitored and reported from the time that the patient provides informed consent and as described in the protocol.
- 19. Study Drug Compliance: The study drug bottle(s) including any unused tablets will be returned to the clinic for drug accountability.
- 20. **Prior/Concomitant Medications and Treatments**: Will be recorded from the time the patient has signed informed consent until 28 days after last treatment. Allowable window for assessment is 0/+7 days. Anti-tumor therapy should be recorded even after 28 days after last treatment.

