- DFS based on IRC review as defined for the primary analysis but instead assigning the dates for events and censoring at the scheduled scan dates instead of the actual scan dates or the date of collection of histo-/cytopathology specimen. Specifically, events that occur within +/- 4 weeks of a scheduled scan will be considered an event at the scheduled scan. Events outside the 4 week window will be counted as events at the next scheduled scan time and censoring outside the 4 week window would be censored at the previous scheduled scan date. If, however, the event is death, the date of death will be used as the event date unless anti-tumor therapy was received prior to the date of death in which case the subject will be censored at the scheduled scan date prior to the date of anti-tumor therapy or for patients who miss 2 or more consecutive

tumor scans immediately followed by an event will be censored at the date of the last objective tumor assessment prior to the missing/not readable scans.

• A parametric model utilizing techniques for interval-censored data will be used to compare the treatment effect.

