**Statistical Analysis Plan**

---

received prior to the date of death in which case the subject will be censored at the scheduled scan prior to the date of anti-cancer therapy or for subjects who have two or more missed or not readable consecutive tumor scans immediately followed by an event will be censored on the date of their most recent scheduled scan prior to the missing/not readable scans. (Refer to Table 6 of Appendix A for censoring rules.)

- DFS with Interval-censoring: DFS based on IRC review as defined for the primary analysis will be performed with a parametric model utilizing techniques for interval-censored data. Graphical diagnostics will be used to select the distribution of the parametric model that best fits the data. Intervals of 16 weeks will be implemented for censoring purposes (Refer to Table 7 of Appendix A for censoring rules.)

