|  | No anti-tumor therapy received after randomization but subject had two or more consecutively missed/not readable IRC reviewed scans immediately prior to recurrence, secondary malignancy or death** | Date of last IRC reviewed scan before two consecutively missed/not readable IRC reviewed scans ** | Yes |

\* Note: For subjects for whom there is site confirmation of recurrence or occurrence of secondary malignancy in the absence of IRC imaging confirmation, the date of IRC confirmation from histo-/cytopathology specimens will be selected as the date of event if available. For subjects for whom the IRC sees a finding on a scan that requires confirmation but an additional scan is not provided, if there is a subsequent pathology report available the pathology report could be the confirmation of the disease seen on the scan. In this case the scan date should be used as the date of recurrence or secondary malignancy.

\*\*Additional details regarding the definition of two or more consecutively missed or inadequate scans can be found in Appendix B. For subjects who died prior to missing two scheduled assessments, they will be coded as an event at the date of death and will not be censored as long as no anti-tumor therapy was given after randomization and before death.

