\*Additional details regarding the definition of two or more consecutively missed scans can be found in Appendix B. For subjects who died prior to missing two scheduled assessments, they will be coded as an event at the date of death and will not be censored as long as no anti-tumor therapy was given after randomization and before death.

**Table 4. Sensitivity Analysis Disease-Free Survival by Independent Review Committee without Censoring Subjects for Anti-tumor Therapy or for two or more consecutively missed or not readable scans**

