## 10. Appendix B

### Data Handling for DFS Events That Occurred after Two or More Consecutively Missed or Not Readable Scans

Section 5.1 of the SAP states the following: “For subjects who had two or more consecutively missed or not readable IRC reviewed scans immediately prior to a recurrence or occurrence of a secondary malignancy or death,

[figure not shown]
- DFS will be censored on the date of the last IRC reviewed scan prior to the consecutively missed or not readable IRC reviewed scans.”

Subjects in this trial are being followed for recurrence or occurrence of a secondary malignancy every 16 weeks during the first 3 years of treatment after randomization and every 6 months after the first 3 years of treatment. Since the frequency of tumor scans varies depending on whether the tumor scan is within 3 years from randomization or after 3 years from randomization, the length of time interval for two consecutively missed tumor scans can be different.

There are 3 scenarios to determine whether a DFS event should be censored due to 2 or more consecutively missed tumor scans. In order to simplify the description of the 3 scenarios, the following abbreviations are defined:

| Definition  | Abbreviation                  |
|---|-------------------------------|
| date of the last evaluable scan prior to the DFS event  | last-non-missing-date         |
| date for the first missed tumor scan that is after the last non-missing tumor scan prior to the DFS event                         | 1 st -missed-date  |
| date for the 2 nd consecutively missed tumor scan that is after the last non-missing tumor scan prior to the DFS event | 2 nd - missed date |
| date of 3 years after randomization date  | 3-Year (YR) rand date         |

(1) The last-non-missing-date is 16 weeks or more before the 3-YR rand date.

In Scenario (1), the targeted date for the 1st-missed-date is 16 weeks after the last-non-missing-date,

|           |   |                 |           |
|-----------|---|-----------------|-----------|
| Document: | C:\Users\q764206\AppData\Local\Microsoft\Windows\Temporary Internet Files\Content.Outlook\GWW33WM3\ATLAS_SAPFinal v8.0_06MAR2018.docx | Version Number: | Final 8.0 |
| Author:   | [name] (Updated [name]; [name]; [name], [name])  | Version Date:   | 06MAR2018 |

Template No: CS\_TP\_BS016 – Revision 2  
 Effective Date: 01Feb2010

[figure not shown]
Reference: CS\_WI\_BS005

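### SAP Table 7 does not implement the promised interval-censored DFS analysis; it codes single dates, censors known events at a midpoint and largely repeats the primary censoring rule

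*SAP*

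**What the plan says.** Protocol 9.2.1 ends its list of DFS sensitivity analyses with this one: "A parametric model utilizing techniques for interval-censored data will be used to compare the treatment effect". SAP 7.3.1 repeats that DFS by IRC will be "performed with a parametric model utilizing techniques for interval-censored data", adds that "Intervals of 16 weeks will be implemented for censoring purposes", and refers to Appendix A, Table 7 for the coding.

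Table 7 has one date column and one Yes/No censoring column. For a confirmed event after two or more scans missed in a row, with no new therapy, the date is "Date of midpoint between last IRC reviewed scan prior to two consecutively missed/not readable scans where there was no IRC confirmed recurrence" and the date of the confirmed event, and the flag is Yes. The two rows for events after new anti-tumor therapy also use a midpoint with Yes. A confirmed event with neither complication is dated when confirmed, with flag No.

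The primary rule (Appendix A, Table 1) censors the same missed-scan events at "Date of last IRC reviewed scan before two consecutively missed/not readable IRC reviewed scans". Table 4 is a separate analysis "without Censoring Subjects for Anti-tumor Therapy or for two or more consecutively missed or not readable scans".

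On timing, Appendix B describes follow-up for recurrence "every 16 weeks during the first 3 years of treatment after randomization and every 6 months after the first 3 years of treatment". The footnotes to the protocol's Schedule of Assessments agree: after year 3, "imaging should be repeated every 6 months for the duration of the DFS follow-up period".

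**The concern.** An interval-censored model needs two dates for each scan-detected event: the last scan that was clear and the scan that showed disease. Table 7 supplies one, which has three consequences.

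- Ordinary recurrences enter as exact on the detection date, so the uncertainty between scans is not modelled.
- Subjects known to have had an event after missed scans or new therapy enter as event-free up to a midpoint. That credits event-free time beyond the last clear scan, and the censoring time is computed from the later event date, so it depends on the outcome.
- The one interval width given, 16 weeks, does not fit scans taken every 6 months.

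At stake is one pre-specified sensitivity analysis. As coded it would agree with the primary analysis almost by construction, and that agreement could be read as support it does not give.

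**Working it through.** **1. Design figures.** The point disputes no number in the plan; these figures are only simulation inputs. From SAP Table 2 the category hazard ratios are ln 0.79 / ln 0.70 = 0.661, ln 0.61 / ln 0.35 = 0.471 and ln 0.51 / ln 0.33 = 0.607. Weighted 0.90, 0.01 and 0.09 they give 0.654, as stated. Freedman's formula, (1.654/0.346)² × (1.960 + 1.282)², gives 241 events against the SAP's 245.

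**2. Table 7 against Table 1.**

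| Situation | Table 1 | Table 7 |
|---|---|---|
| No event, scanned after baseline | last scan, censored | same |
| No event, never scanned after baseline | randomization, censored | same |
| Disease on baseline scan | randomization, event | same |
| Event, no therapy, no run of missed scans | event date, event | same |
| Event after missed scans | last scan before gap, censored | midpoint, censored |
| Event after new therapy | last scan before therapy, censored | midpoint, censored |
| Event after both | last scan before both, censored | midpoint, censored |

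Status agrees in 7 of 7 rows and the date in 4 of 7. The other three only move the censoring date.

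**3. What the likelihood needs.** With an exponential model, an exact event at t contributes λe^(−λt), a right-censored subject e^(−λc), and an event in (L, R] contributes e^(−λL) − e^(−λR). Take a category 1 placebo subject with λ = −ln 0.70 / 104 = 0.00343 per week, clear at week 48, scans at weeks 64 and 80 missed, recurrence seen at week 96.

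- Interval coding: e^(−0.165) − e^(−0.329) = 0.848 − 0.719 = 0.129, the probability of an event in weeks 48 to 96.
- Table 7: censored at (48 + 96)/2 = week 72, contributing e^(−0.247) = 0.781, the probability of no event by week 72. The known event is discarded and 24 unobserved weeks are counted as event-free.

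**4. Gap widths.** Appendix B treats an event as following two missed scans only if it is more than 16 + 16 + 2 = 34 weeks (Scenario 1) or 16 + 26 + 2 = 44 weeks (Scenario 2) after the last evaluable scan. The midpoint is then more than 17 or 22 weeks past that scan. No 16-week interval can hold such a gap.

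**5. Simulation.** 2000 replicates per setting; 700 subjects 1:1; risk mix 90/1/9%; SAP Table 2 rates (design) or placebo rates in both arms (null); uniform accrual over 24 months; 23% drop-out by 18 months; scans every 16 weeks to week 160, then every 26 weeks; cut at 245 primary-rule events. Runs of two missed scans are independent of event time. The share of events affected is an assumption. All codings are fitted by exponential regression on treatment and risk category. Geometric-mean HR, Monte Carlo SE at most 0.003:

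| Truth; affected events, placebo/axitinib | Interval | Table 4 | Primary | Table 7 |
|---|---|---|---|---|
| Null; 0/0 | 1.002 | 1.002 | 1.002 | 1.002 |
| Null; 10%/10% | 0.997 | 0.997 | 0.997 | 0.997 |
| Null; 5%/15% | 0.998 | 0.989 | 0.906 | 0.895 |
| Null; 15%/5% | 0.998 | 1.007 | 1.097 | 1.111 |
| Design; 0/0 | 0.646 | 0.655 | 0.655 | 0.655 |
| Design; 10%/10% | 0.648 | 0.660 | 0.654 | 0.657 |
| Design; 5%/15% | 0.647 | 0.654 | 0.589 | 0.585 |
| Design; 15%/5% | 0.648 | 0.665 | 0.724 | 0.735 |

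In the null 10%/10% setting the category 1 placebo hazard relative to truth is 1.004 (interval), 0.885 (primary) and 0.877 (Table 7). Recurrences detected after week 160, on the 26-week schedule, are 12% under design rates and 3% under the null.

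A separate, smaller simulation (150 replicates per setting, with both missed scans and new therapy) gave primary and Table 7 log HRs correlated at 0.999 or higher.

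**The case against.** The strongest reply is that Table 7 must be read with SAP 7.3.1: the table gives a date, the text gives a 16-week width, and Yes may mean interval-censored. On that reading the bias goes. In a 250-replicate null run with about 6% of placebo and 17% of axitinib events affected, 16-week intervals centred on the midpoint gave 0.997, against 0.880 for the literal coding. The reading does not survive the table. Its first two rows use the same Yes for event-free subjects, who are right-censored. Ordinary recurrences stay No. A 16-week width cannot span gaps of more than 34 or 44 weeks.

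Four other points stand, at least in part.

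- Most of the contrast comes from counting events after missed scans, not from the interval likelihood. With primary censoring kept, a correct (L, R] model gave 0.904 against 0.907 for primary coding (null, about 5% and 14% affected). Table 4 already counts those events.
- The 16-week width hardly matters numerically: 0.644 with fixed intervals, 0.643 with actual ones (design rates, no missed scans).
- The main simulation has no new therapy, and the replacement keeps the primary censoring for it. In the smaller simulation, therapy before the event in 5% and 20% of events gave 0.551 under Table 7 and 0.644 when those events were counted. The fix would not close that gap.
- The Table 7 header carries an asterisk whose note is absent from the text available, so an explanation may have been lost. A note would still not supply a second date column.

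**Conclusion.** The point holds. As written, Table 7 is not an interval-censored analysis: it has no bounds, treats scan-detected recurrences as exact, and records known events as event-free to a date derived from the event. It reproduces the primary rule's event status throughout, so it cannot test that rule.

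The size is modest and conditional. Exact dating alone moves the HR by under 0.01 (0.646 to 0.655). Equal missed-scan shares leave the null HR at 1.00, though the placebo hazard is about 12% too low under both the primary rule and Table 7. Unequal shares of 5% and 15% move a null HR to 0.895 or 1.111 depending on direction, nearly all of it inherited from the primary rule. Those shares are assumptions; the documents give none.

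The primary test, alpha, stopping rule and 245-event target are untouched. Tables 4 and 5 test the censoring and Table 6 addresses scan timing, so the loss is confined to this one analysis. It should be corrected, but it does not threaten the trial's main conclusion.

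**What to change.** Replace Table 7 with a table giving L and R for each situation, from actual scan or specimen dates:

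- **Recurrence or secondary malignancy:** L = last negative IRC-read scan, R = date of the scan or specimen that showed it, including events found after missed scans.
- **Death:** exact, at the date of death.
- **No event:** right-censored at the last negative scan.
- **Disease on the baseline scan:** event at randomization, as now.
- **New anti-tumor therapy before an event:** right-censored at the last negative scan before therapy, as in the primary analysis.

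Remove the midpoints. In SAP 7.3.1, replace the fixed 16-week sentence with one stating that intervals come from actual dates, that missed-scan events are counted through their wider interval, and that any bias from censoring at new therapy is left to Tables 4 and 5.

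The cost is one SAP table and one sentence. All the dates are already collected, and the primary analysis and alpha do not change. Make the change before unblinding, so that the coding is not chosen with results in view.

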## 10. Appendix B

### Data Handling for DFS Events That Occurred after Two or More Consecutively Missed or Not Readable Scans

Section 5.1 of the SAP states the following: “For subjects who had two or more consecutively missed or not readable IRC reviewed scans immediately prior to a recurrence or occurrence of a secondary malignancy or death,

[figure not shown]
- DFS will be censored on the date of the last IRC reviewed scan prior to the consecutively missed or not readable IRC reviewed scans.”

Subjects in this trial are being followed for recurrence or occurrence of a secondary malignancy every 16 weeks during the first 3 years of treatment after randomization and every 6 months after the first 3 years of treatment. Since the frequency of tumor scans varies depending on whether the tumor scan is within 3 years from randomization or after 3 years from randomization, the length of time interval for two consecutively missed tumor scans can be different.

There are 3 scenarios to determine whether a DFS event should be censored due to 2 or more consecutively missed tumor scans. In order to simplify the description of the 3 scenarios, the following abbreviations are defined:

| Definition  | Abbreviation                  |
|---|-------------------------------|
| date of the last evaluable scan prior to the DFS event  | last-non-missing-date         |
| date for the first missed tumor scan that is after the last non-missing tumor scan prior to the DFS event                         | 1 st -missed-date  |
| date for the 2 nd consecutively missed tumor scan that is after the last non-missing tumor scan prior to the DFS event | 2 nd - missed date |
| date of 3 years after randomization date  | 3-Year (YR) rand date         |

(1) The last-non-missing-date is 16 weeks or more before the 3-YR rand date.

In Scenario (1), the targeted date for the 1st-missed-date is 16 weeks after the last-non-missing-date,

|           |   |                 |           |
|-----------|---|-----------------|-----------|
| Document: | C:\Users\q764206\AppData\Local\Microsoft\Windows\Temporary Internet Files\Content.Outlook\GWW33WM3\ATLAS_SAPFinal v8.0_06MAR2018.docx | Version Number: | Final 8.0 |
| Author:   | [name] (Updated [name]; [name]; [name], [name])  | Version Date:   | 06MAR2018 |

Template No: CS\_TP\_BS016 – Revision 2  
 Effective Date: 01Feb2010

[figure not shown]
Reference: CS\_WI\_BS005

Statistical Analysis Plan

---

and the targeted date for the 2nd-missed-date is 32 weeks after the last non-missing-date. After adding a 2-week window, the decision rule is: if the DFS event is >34 weeks after the last non-missing date, DFS time will be censored at the date of the last non-missing tumor scan prior to the DFS event, otherwise DFS time will be the non-censored time interval from randomization date to the date of DFS event.

- (2) The last-non-missing-date is before the 3-YR rand date, but the last-non-missing-date plus 16 weeks is beyond the 3-YR rand date.

In Scenario (2), the targeted date for the 1st-missed-date is 16 weeks after the last-non-missing-date, and the targeted date for the 2nd-missed-date is 16 weeks plus 26 weeks after the last-non-missing-date. After adding a 2-week window, the decision rule is: if the DFS event is >44 weeks) after the last-non-missing-date, DFS time will be censored at the date of the last non-missing tumor scan prior to the DFS event, otherwise DFS time will be the non-censored time interval from the randomization date to the date of DFS event.

- (3) The last-non-missing-date is beyond the 3-YR rand date.

---

Document: C:\Users\q764206\AppData\Local\Microsoft\Windows\Temporary Internet Files\Content.Outlook\GWW33WM3\ATLAS\_SAPFinal v8.0\_06MAR2018.docx  
 Author: [name] (Updated [name]; [name]; [name], [name])      Version Number: Final 8.0

Version Date: 06MAR2018

Template No: CS\_TP\_BS016 – Revision 2  
 Effective Date: 01Feb2010

Reference: CS\_WI\_BS005

Statistical Analysis Plan

---

Partial dates should be presented as --NOV1999 or - - - - - 1999 as needed.

Partial times should be presented as --:30 or 14:-- as needed.

Listings should be sorted according to the order of the columns.

---

|           |   |                 |           |
|-----------|---|-----------------|-----------|
| Document: | C:\Users\q764206\AppData\Local\Microsoft\Windows\Temporary Internet Files\Content.Outlook\GWW33WM3\ATLAS_SAPFinal v8.0_06MAR2018.docx |                 |           |
| Author:   | [name] (Updated [name]; [name]; [name], [name])  | Version Number: | Final 8.0 |
|           |   | Version Date:   | 06MAR2018 |

Template No: CS\_TP\_BS016 – Revision 2  
Effective Date: 01Feb2010

Reference: CS\_WI\_BS005

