| Document: | C:\Users\q764206\AppData\Local\Microsoft\Windows\Temporary Internet Files\Content.Outlook\GWW33WM3\ATLAS_SAPFinal v8.0_06MAR2018.docx |                 |           |
| Author:   | [name] (Updated [name]; [name]; [name], [name])  | Version Number: | Final 8.0 |
|           |   | Version Date:   | 06MAR2018 |

Template No: CS\_TP\_BS016 – Revision 2  
 Effective Date: 01Feb2010

Reference: CS\_WI\_BS005

Statistical Analysis Plan

---

For subjects with no DFS event, DFS time will be censored

- at the date of last IRC reviewed scan prior to the time of the final analysis.
- Subjects alive who do not have any post-baseline disease assessments will have their DFS times censored at randomization.

For any subject who receives anti-tumor therapy,

- DFS will be censored on the date of the last IRC reviewed scan prior to taking the anti-tumor therapy. However, in cases where there is no scan prior to anti-cancer therapy medication that was received after randomization, subjects will be censored at the date of randomization.

For subjects who had two or more consecutively missed or not readable IRC reviewed scans immediately prior to a recurrence or occurrence of a secondary malignancy or death,

- DFS will be censored on the date of the last IRC reviewed scan prior to the consecutively missed or not readable IRC reviewed scans.

The length of DFS will be calculated as follows:

$$\text{DFS (years)} = [\text{date of recurrence, secondary malignancy, or death or censor date} - \text{randomization date} + 1] / 365.25.$$

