## 9. Appendix A

**Table 1. Primary Endpoint Disease-Free Survival by Independent Review Committee Censoring Rules:**

|  |  | Date of event*/ censoring  | Censoring |
|--|--|---|------------------|
| No IRC confirmed recurrence or occurrence of secondary malignancy or death | Post baseline assessments performed  | Date of last IRC reviewed scan prior to receiving anti-tumor therapy, if applicable   | Yes              |
|  | No post baseline assessments performed   | Date of randomization   | Yes              |
| IRC confirmed recurrence, secondary malignancy or death                    | Baseline scan shows presence of disease  | Date of randomization   | No               |
|  | Further anti-tumor therapy received after randomization and before recurrence or occurrence of secondary malignancy or death (Subject does not have two or more consecutively missed/not readable IRC reviewed scans immediately prior to recurrence, secondary malignancy or death)** | Date of last IRC reviewed scan prior to receiving anti-tumor therapy  | Yes              |
|  | Further anti-tumor therapy received after randomization and before recurrence or occurrence of secondary malignancy or death and subject had two or more consecutively missed/not readable IRC reviewed scans immediately prior to recurrence, secondary malignancy or death)**        | Date of last IRC reviewed scan prior to the two consecutively missed/not readable scans and prior to receiving anti-tumor therapy** | Yes              |
|  | No anti-tumor therapy received after randomization (Subject does not have two or more consecutively missed/not readable IRC reviewed scans immediately prior to recurrence, secondary malignancy or  | Date of IRC confirmed recurrence or occurrence of secondary malignancy or death, whichever occurred first*                          | No               |

Document: C:\Users\q764206\AppData\Local\Microsoft\Windows\Temporary Internet Files\Content.Outlook\GWW33WM3\ATLAS\_SAPFinal v8.0\_06MAR2018.docx

Author: [name] (Updated [name]; [name]; [name], [name])

Version Number:

Final 8.0

Version Date:

06MAR2018

Template No: CS\_TP\_BS016 – Revision 2  
 Effective Date: 01Feb2010

Reference: CS\_WI\_BS005

Statistical Analysis Plan

|  |  |   |     |
|--|--|---|-----|
|  | death)**   |   |     |

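### SAP Appendix B, Scenario (1): when the baseline scan is the only evaluable scan before the event, the 34-week limit can censor a recurrence after one missed scan, at a date before randomization

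*SAP*

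**What the plan says.** SAP 5.1 bases censoring on a count of missed scans. It applies "For subjects who had two or more consecutively missed or not readable IRC reviewed scans immediately prior to a recurrence or occurrence"; second cancers and deaths are treated alike. The censoring date is the last IRC reviewed scan before the gap.

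Appendix A, Table 1 repeats the count. Its event row reads "No anti-tumor therapy received after randomization (Subject does not have two or more consecutively missed/not readable IRC reviewed scans immediately prior to recurrence", and its censored row uses the "Date of last IRC reviewed scan before two consecutively missed/not readable IRC reviewed scans". Both rows carry a footnote: "Additional details regarding the definition of two or more consecutively missed or inadequate scans can be found in Appendix B".

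Appendix B replaces the count with elapsed time. It starts from the "date of the last evaluable scan prior to the DFS event". In Scenario (1), where that scan is at least 16 weeks before the third anniversary of randomization, the two missed scans are targeted at 16 and 32 weeks after it and a 2-week window is added. The rule is then "if the DFS event is >34 weeks after the last non-missing date, DFS time will be censored", at the date of that last scan.

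SAP 5.1 falls back on the randomization date in two other situations. One is for subjects without a DFS event: "Subjects alive who do not have any post-baseline disease assessments will have their DFS times censored at randomization". The other is for anti-tumor therapy, "in cases where there is no scan prior to anti-cancer therapy medication that was received after randomization". Neither is repeated for the missed-scan rule.

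**The concern.** The limit assumes that the next scan was due 16 weeks after the anchor scan. That holds for an on-study scan. It does not hold for the baseline scan, because the protocol schedules on-study imaging from first dose (Schedule of Assessments, footnote 14; Section 3). Any time between the baseline scan and first dose uses up part of the 34 weeks before the first on-study scan is due.

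Two things follow for a patient with no evaluable post-baseline scan before the event. First, one missed scan can be treated as two, so an IRC-confirmed recurrence that SAP 5.1 counts as an event is censored in the primary analysis. Second, the assigned censoring date is the baseline scan, which precedes randomization, so the SAP 5.1 formula gives a negative DFS time. The second fault also arises when two scans really were missed after baseline.

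**Working it through.** **Inputs**
- Limit: more than 34 weeks from the last evaluable scan (SAP Appendix B, Scenario 1).
- Baseline scan: weeks 3 to 8 after nephrectomy (Protocol 7.1), IRC reviewed (Schedule of Assessments, footnote 14).
- Randomization: weeks 4 to 12 after nephrectomy; first dose within 7 days of randomization (Protocol 4.3).
- On-study scans: every 16 weeks from first dose, ±7 days (footnote 14).
- DFS in years = (event or censoring date − randomization date + 1)/365.25 (SAP 5.1).

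**1. The plan's figure.** 16 + 16 + 2 = 34 weeks.

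**2. It works for a post-baseline anchor.** With one scan missed, the next attended scan is 32 weeks after the anchor. With ±1 week at each end it lies at 30 to 34 weeks, never beyond 34, so the event is kept.

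**3. A baseline anchor.** Let L be the time from baseline scan to first dose. The largest permitted value is (12 − 3) + 1 = 10 weeks. Counted from first dose, the limit falls at 34 × 7 − L = 238 − L days:

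| L (days) | Limit, days after first dose | Weeks after first dose |
|---|---|---|
| 14 | 224 | 32 |
| 28 | 210 | 30 |
| 42 | 196 | 28 |
| 70 | 168 | 24 |

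The week-32 scan is at day 224. A recurrence found there, with only the week-16 scan missed or unreadable, is censored when 224 + L > 238, that is, L > 14 days. If the scan is 7 days late the condition is L > 7; if 7 days early, L > 21.

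**4. How often the permitted dates give such a gap.** As an assumption, take every permitted combination as equally likely: scan on day 21 to 56, randomization on day 28 to 84 and not before the scan, first dose 0 to 7 days later. Then L > 14 in 76.5% of combinations (L > 7 in 91.4%, L > 21 in 61.2%). This describes the calendar within the edge case, not the share of trial patients affected.

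**5. The resulting DFS time.**
- Scan in week 8, randomization in week 12 (28 days later): (−28 + 1)/365.25 = −0.074 years.
- Scan in week 3, randomization in week 12 (63 days later): (−63 + 1)/365.25 = −0.170 years.
- The same recurrence counted as an event at the week-32 scan: (224 + 1)/365.25 = 0.616 years if dosed on the day of randomization, (231 + 1)/365.25 = 0.635 years if dosed 7 days later.

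**6. Check of the proposed change.** Counted from first dose, the latest on-window week-32 scan is at (224 + 7)/7 = 33 weeks, which is within 34, so the event is kept for any L. Counted from randomization in a treated patient, the latest case is (7 + 224 + 7)/7 = 34.0 weeks. That passes with no margin, and dosing one day late would bring the fault back.

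**The case against.** The best counter-argument is that the SAP means post-baseline scans throughout. The anti-tumor therapy fallback in SAP 5.1 provides for subjects with no prior scan, although every randomized subject should have a baseline scan, so the word there probably means a post-baseline scan. Appendix B's title also confines it to events after two or more missed scans, and a patient who attended week 32 missed only one. As a reading of intent this is plausible. It is not written into Appendix B, whose anchor carries no such limit. If it were the meaning, this patient would have no anchor date at all in the available text.

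Part of Appendix B, from Scenario (3) onward, is not in the text available, and a note on such patients could stand there. It therefore cannot be said that the plan as a whole is silent. Scenario (1)'s own decision rule is complete, however, and gives this result as written.

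A reader might extend the point in three ways that the documents do not support.
- *Deaths are wrongly censored too.* The Table 1 footnote already keeps deaths before two missed assessments as events, provided no anti-tumor therapy came first.
- *Scenario (2)'s 44 weeks fails for patients who complete 3 years of treatment.* That needs their last scan to fall before the third anniversary of randomization, which rests on an inferred treatment length or an early scan. The neighbouring Scenario (3) limit cannot be seen.
- *The treatment comparison is biased or power is lost.* Nothing points to an imbalance between arms, and the final analysis waits for about 245 counted events (SAP 7.1.1).

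**Conclusion.** The point holds as a minor edge case in which a written rule for the primary endpoint gives the wrong result. It needs all of the following: no evaluable scan between baseline and the event, no earlier anti-tumor therapy, a baseline scan more than about 14 days before first dose (7 to 21 with the scan window), and a recurrence or secondary malignancy first found around the week-32 scan. The negative DFS time needs less: a baseline-only anchor and any censoring under the missed-scan rule.

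How many patients meet these conditions cannot be derived from the documents; few is the reasonable expectation. Additional imaging when recurrence is suspected and the scan at withdrawal from treatment (Protocol 6.2.2 and 6.2.3) will give many patients a later anchor. The Table 4 sensitivity analysis does not censor for missed scans and so keeps these events. The conclusion rests on applying the available Appendix B text literally.

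**What to change.** Add to Appendix B: where there is no evaluable post-baseline scan before the event, the 34 weeks are counted from first dose (from randomization only if the subject was never treated), and if the event is censored under this rule the censoring date is randomization. An on-window week-32 recurrence after one missed scan then stays an event, and no DFS time is negative. Appendix A, Tables 3 and 5, also refer to Appendix B, so the same wording should be carried through to them. The cost is a few lines of SAP text and programming, with no new data. It should be settled before unblinded results are seen.
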